6.5.4 Documentation of prior and new concomitant therapies

Any medication or vaccine (including over-the-counter or prescription medicines, vitamins, and/or herbal supplements) that the participant is receiving at the time of enrollment or receives during the study must be recorded along with:

- Reason for use
- Dates of administration including start and end dates
- Dosage information including dose and frequency

The Medical Monitor should be contacted if there are any questions regarding concomitant or prior therapy.

6.6 Dose Modification

In case a dose reduction is necessary, the study treatment will be administered according to the following tables. [Table 6-1](#) shows the dose modification levels for regorafenib. [Table 6-2](#), [Table 6-3](#), [Table 6-4](#), and [Table 6-5](#) show the dose modification plans for specific known drug-related toxicities.

Table 6-1: Dose modification levels for regorafenib

Dose Level	Daily Dose	Number of tablets
Dose level 0 (standard dose)	160 mg	4 tablets of regorafenib, 40 mg-tablet
Dose level -1	120 mg	3 tablets of regorafenib, 40 mg-tablet
Dose level -2	80 mg	2 tablets of regorafenib, 40 mg-tablet

Table 6-2: Dose Modification/Delay for Toxicities Related to Study Drug (Except Hand Foot Skin Reaction, Hypertension, and ALT and/or AST increases)^{a,c}

Grade of Event	Dose Interruption	Dose modification	Dose for subsequent cycles
Grade 0-2	Treat on time	No change	No change
Grade 3	Delay until \leq Grade 2 ^b	Reduce 1 dose level	If toxicity remains \leq Grade 2, dose re-escalation can be considered at the discretion of the treating investigator. If dose is re-escalated and toxicity (\leq Grade 3) recurs, institute permanent dose reduction.
Grade 4	Delay until \leq Grade 2 ^b	Reduce by 1 dose level. Permanent discontinuation can be considered at treating investigator's discretion.	

Abbreviations: ALT – alanine transaminase; AST – aspartate transaminase

a Excludes alopecia, non-refractory nausea/vomiting, non-refractory hypersensitivity, non-clinically significant and asymptomatic laboratory abnormalities.

b If no recovery after a 4-week delay, treatment should be permanently discontinued. In the event of severe bleeding necessitating urgent medical intervention, permanent discontinuation of regorafenib should be considered.

c In subjects who develop cardiac ischemia and/or infarction, interruption of regorafenib is recommended until resolution. The decision to re-initiate regorafenib therapy should be based on careful consideration of the potential benefits and risks of the individual subject. Regorafenib should be permanently discontinued if there is no resolution.

Table 6-3: Dose modifications for HFSR related to regorafenib (dose expansion phase) ("Palmar-plantar erythrodysesthesia syndrome")

Skin toxicity grade	Occurrence	Recommended dose modification and measures
Grade 1: Numbness, dysesthesia, paresthesia, tingling, painless swelling, erythema or discomfort of the hands or feet which does not disrupt the subject's normal activities	Any	Maintain dose level and immediately institute supportive measures for symptomatic relief.
Grade 2: Painful erythema and swelling of the hands or feet and/or discomfort which affects the subject's normal activities.	1 st occurrence	Decrease dose by 40 mg (one tablet) and immediately institute supportive measures. If no improvement occurs despite dose reduction, interrupt therapy for a minimum of 7 days, until toxicity resolves to Grade 0-1. A dose re-escalation is permitted at the discretion of the treating physician.
	No improvement within 7 days or 2 nd occurrence	Interrupt therapy until toxicity resolves to Grade 0-1. When resuming treatment, decrease dose by 40 mg (one tablet). A dose re-escalation is permitted at the discretion of the treating physician.
	3 rd occurrence	Interrupt therapy until toxicity resolves to Grade 0-1. When resuming treatment, decrease dose by 40 mg (one tablet). A dose re-escalation is permitted at the discretion of the treating physician.
	4 th occurrence	Discontinue treatment.
Grade 3: Moist desquamation, ulceration, blistering or severe pain of the hands or feet, or severe discomfort that causes the subject to be unable to work or perform activities of daily living.	1 st occurrence	Institute supportive measures immediately. Interrupt therapy for a minimum of 7 days until toxicity resolves to Grade 0-1. When resuming treatment, decrease dose by 40 mg (one tablet). A dose re-escalation is permitted at the discretion of the treating physician.
	2 nd occurrence	Institute supportive measures immediately. Interrupt therapy for a minimum of 7 days until toxicity resolves to Grade 0-1. When resuming treatment, decrease dose by 40 mg (one tablet).
	3 rd occurrence	Discontinue treatment.

Abbreviations: HFSR – hand-foot-skin reaction

Table 6-4: Recommended dose modification and measures for hypertension

Hypertension grade	Occurrence	Recommended dose modification and measures ^a
Grade 1	Any	Maintain dose level. Consider increased BP monitoring.
Grade 2	Any	Institute antihypertensive treatment with the aim to achieve diastolic BP \leq 90 mmHg: 
 • If BP previously within normal limits, start antihypertensive monotherapy. • If subject already on antihypertensive medication, titrate up the dose. Continue regorafenib, or if symptomatic, hold regorafenib until symptoms resolve AND diastolic BP \leq 90 mmHg. ^b When regorafenib is restarted, continue at the same dose level.
Grade 3	First occurrence	Institute antihypertensive treatment with the aim to achieve diastolic BP \leq 90 mmHg: 
 • Start antihypertensive medication AND/OR 
 • Increase current antihypertensive medication AND/OR 
 • Add additional antihypertensive medications. Hold regorafenib until diastolic BP \leq 90 mm Hg, and if symptomatic, until symptoms resolve. ^b When regorafenib is restarted, continue at the same dose level. If BP is not controlled with the addition of new or more intensive therapy, reduce by 1 dose level. ^c
	Re-occurrence	If Grade 3 hypertension recurs despite dose reduction and antihypertensive therapy, reduce another dose level. ^d
Grade 4	Any	Discontinue therapy

Abbreviations: BP = blood pressure.

a A more conservative management of hypertension is allowed if judged medically appropriate by the investigator.

b Subjects requiring a delay of >4 weeks should go off regorafenib.

c If BP remains controlled for at least one full cycle, dose re-escalation is permitted at the investigator's discretion.

d Subjects requiring >2 dose level reductions (<80 mg reduction) should go off regorafenib.

Table 6-5: Dose modification/interruption for ALT/AST increases related to regorafenib

Observed elevations of ALT and / or AST	Occurrence	Recommended measures and dose modification
≤5 times ULN	Any occurrence	Continue regorafenib treatment. Monitor liver function weekly until transaminases return to <3 times ULN or baseline.
>5 times ULN to ≤20 times ULN	1 st occurrence	Interrupt regorafenib treatment. Monitor transaminases weekly until return to <3 times ULN or baseline. Restart: If the potential benefit outweighs the risk of hepatotoxicity, re-initiate regorafenib treatment, reduce dose by 40 mg (one tablet), and monitor liver function weekly for at least 4 weeks.
	Re-occurrence	Discontinue treatment with regorafenib permanently.
>20 times ULN	Any occurrence	Discontinue treatment with regorafenib permanently.
>3 times ULN with concurrent bilirubin >2 times ULN	Any occurrence	Discontinue treatment with regorafenib permanently. Monitor liver function weekly until resolution or return to baseline. Exception: patients with Gilbert's syndrome who develop elevated transaminases should be managed as per the above outlined recommendations for the respective observed elevation of ALT and / or AST.

Abbreviations: ALT – alanine transaminase; AST – aspartate transaminase; ULN = upper limit of normal.

If a dose reduction has been performed within this study protocol intra subject dose reescalation can be considered up to the starting dose in this rollover study protocol at the discretion of the treating physician.

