5.4 Screen Failures

Screen failures are defined as participants who consent to participate in the clinical study but are not subsequently entered in the study. A minimal set of screen failure information is required to ensure transparent reporting of screen failure participants to meet the Consolidated Standards of Reporting Trials (CONSORT) publishing requirements and to respond to queries from regulatory authorities. Minimal information includes demography, screen failure details, eligibility criteria, and any SAE.

Individuals who do not meet the criteria for participation in this study (screen failure) may not be rescreened.

6. Study Intervention

The following investigational products will be used in the study:

- Regorafenib, 20 mg tablets
- Regorafenib, 40 mg tablets

Participants will be treated with the regorafenib dose taken during the last cycle of the feeder study. They will receive either 60, 80, 120, or 160 mg orally (p.o.) every day (qd) for 3 weeks of every 4 week cycle (i.e. 3 weeks on, 1 week off).

Study drug should be taken within 2 hours after a light meal with approximately 240 mL (8 fluid ounces) of water, preferably in the morning. If necessary, the study drug may be taken at different times of the day, but there should be consistency with respect to dosing intervals (the recommendation is to have at least a 20 hour interval between doses).

If a dose of study drug will be missed, the missed dose should be skipped (vomited tablets cannot be made up), and the next dose should be taken at the regular time. The subsequent dose of study drug should not be doubled. The investigator should be informed if the dose of regorafenib taken exceeded the scheduled dose.

Regorafenib will be provided by the sponsor as tablets.

The regorafenib 40 mg tablet is coated, not divisible, gray-orange-red, oval (length 16 mm, width 7, thickness 4.9-5.6) and 472 mg each in total weight. The 40 mg tablets are embossed with "40" on one side of the tablet, and "BAYER" on the other side. The packaging configuration is 30 tablets regorafenib 40mg and a 3 g desiccant capsule per bottle of regorafenib 40 mg.

The regorafenib 20 mg tablet is coated, not divisible, gray-orange-red, round, biconvex (diameter 9mm, thickness 3.5-4.0mm) and 238 mg each in total weight. The 20 mg tablets are not coded.

The packaging configuration is 65 tablets regorafenib 20 mg and a 3 g desiccant capsule per bottle of regorafenib 20 mg.

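### Entry is allowed at 60, 80, 120 or 160 mg, but the dose-reduction and stopping rules give a workable path only from 160 mg (two steps) and 120 mg (one step)

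*Protocol*

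**What the plan says.** Section 6 carries the last feeder dose forward: "They will receive either 60, 80, 120, or 160 mg orally (p.o.) every day (qd) for 3 weeks of every 4 week cycle". Two tablet strengths are supplied, including "Regorafenib, 20 mg tablets".

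Section 6.6 makes its own tables govern any reduction: "In case a dose reduction is necessary, the study treatment will be administered according to the following tables". Within those tables:

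- Table 6-1 lists 160, 120 and 80 mg. The lowest row, level -2, is "2 tablets of regorafenib, 40 mg-tablet".
- Table 6-2 (general toxicity, Grade 3) says "Reduce 1 dose level". Table 6-4 (hypertension) also works in levels: "If Grade 3 hypertension recurs despite dose reduction and antihypertensive therapy, reduce another dose level".
- Table 6-3 (hand-foot skin reaction, HFSR) uses a fixed step. For the second and again for the third Grade 2 occurrence it says "Interrupt therapy until toxicity resolves to Grade 0-1. When resuming treatment, decrease dose by 40 mg (one tablet"; only the fourth occurrence stops treatment. Table 6-5 (ALT/AST) uses the same 40 mg step, once.
- Footnote d of Table 6-4 sends patients off drug after more than two level reductions and adds a parenthesis that mentions 80 mg.
- The closing sentence of 6.6 caps re-escalation at the rollover starting dose. It sets no lower limit.

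Section 7.1 makes withdrawal mandatory when more than two reductions are needed. It gives no minimum dose and no dose from which to count. It also says that permanent discontinuation ends participation.

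**The concern.** A site that follows the written rules for a 60 or 80 mg entrant reaches a level that does not exist or a dose that is not listed. For a third Grade 2 HFSR it can receive two opposite instructions. The site must then choose between stopping the drug and giving a dose outside the protocol.

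Both outcomes matter. Stopping ends access, and continued access is the first primary objective (Section 3). An unlisted dose has no basis in the protocol. The choice also affects reporting: the same toxicity can be counted as a dose modification, which is the secondary endpoint, or appear under discontinuations.

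**Working it through.** The plan has no figure of its own to reproduce, since there is no sample size calculation and no hypothesis test (Sections 9.1 and 9.2). The check is to follow each permitted entry dose through the rules.

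**Inputs.** Entry doses 60, 80, 120 and 160 mg (Section 6); levels 160, 120 and 80 mg (Table 6-1); step of one level (Tables 6-2 and 6-4) or 40 mg (Tables 6-3 and 6-5); withdrawal if more than two reductions are needed (Section 7.1).

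**Step 1: levels available.** Count the Table 6-1 rows below the entry dose. **Step 2: 40 mg steps.** Subtract 40 mg from the entry dose, without re-escalation, and stop at the first unlisted dose.

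| Entry dose | Levels below it in Table 6-1 | 40 mg steps |
|---|---|---|
| 160 mg | 2 (120, 80) | 160 - 40 = 120, listed; 120 - 40 = 80, listed; 80 - 40 = 40, unlisted |
| 120 mg | 1 (80) | 120 - 40 = 80, listed; 80 - 40 = 40, unlisted |
| 80 mg | 0 | 80 - 40 = 40, unlisted |
| 60 mg | not defined, no row | 60 - 40 = 20, unlisted |

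The first 40 mg step lands on a listed dose for 2 of the 4 entry doses, and the second for 1 of 4.

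**Step 3: what Section 7.1 adds.** The text allows two origins for the count.

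- *Counted from 160 mg (level 0).* A 120 mg entrant has used (160 - 120)/40 = 1 reduction and an 80 mg entrant (160 - 80)/40 = 2. The next reduction for the 80 mg entrant is the third, so withdrawal is mandatory. For 60 mg, (160 - 60)/40 = 2.5, which is not a whole number of steps, so the count is undefined.
- *Counted from the rollover starting dose.* Every entrant begins at 0. An 80 mg entrant needing a first reduction does not meet the 7.1 criterion, yet Table 6-1 offers no level and Tables 6-3 and 6-5 point to 40 mg.

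For an 80 mg entrant the two readings therefore lead to opposite actions.

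**Step 4: third Grade 2 HFSR.** From 160 mg without re-escalation, Table 6-3 gives 120 mg, then 80 mg, then resumption at 40 mg. That is a third reduction, for which Section 7.1 requires withdrawal. If the dose was re-escalated in between, the count is unclear, because 7.1 does not say whether a reversed reduction still counts.

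**Step 5: footnote d.** Two level reductions from 160 mg amount to 80 mg, so more than two would exceed 80 mg. The parenthesis says less than 80 mg. It may have been meant as a floor of 80 mg, but it does not say so and it applies to hypertension only.

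**The case against.** The best defence is that 80 mg is the implied floor. If 7.1 counts from the standard 160 mg dose, the three-row table, the limit of two reductions and the 80 mg in footnote d all agree, and an 80 mg entrant who needs a reduction simply stops. This is a reasonable reading, and it means nobody can assert that 7.1 is plainly unmet at such a participant's first rollover reduction. But the text does not state it, and it leaves the permitted 60 mg entry dose without a place.

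The modification columns of Tables 6-3 to 6-5 are headed as recommendations, whereas 7.1 is mandatory, so 7.1 can be said to prevail at the third Grade 2 HFSR. That is fair as interpretation. Even so, Table 6-3 tells the site to resume and to stop only at the fourth occurrence, and the opening of 6.6 says the tables apply.

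The Schedule of Activities refers dosing to the feeder protocol, which might define lower levels. Those protocols are not available here, and 6.6 points to its own tables for reductions. Investigator discretion (7.1) and discussion of immediate safety concerns with the sponsor (Section 8) allow individual decisions but supply no dose, and Section 8 excludes waivers.

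A reader might infer more than the documents support:

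- That the protocol prescribes a dose of zero or below. Continuing the subtraction gives such numbers, but they are not regimens; reaching zero means stopping.
- That a single unresolved Grade 2 HFSR episode always costs two 40 mg decreases, because the second row also covers "No improvement within 7 days". This is a literal reading, and the point does not need it.
- That 40 mg and one tablet disagree at 60 mg. The documents do not say how 60 mg is made up; with one 40 mg and one 20 mg tablet the two agree.
- That the secondary endpoint is compromised. Discontinuations and their reasons are reported separately (SAP 4.3 and 6.6), so the effect is inconsistent classification in descriptive tables.

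**Conclusion.** The point holds. Sections 6, 6.6 and 7.1 fit together within Table 6-1 for two reductions from 160 mg and one from 120 mg. At 80 and 60 mg a one-level reduction is undefined and the 40 mg step gives an unlisted dose (40 or 20 mg); the second 40 mg step from 120 mg also gives 40 mg. Whether 7.1 requires an 80 mg entrant to stop depends on a count origin that is not stated. The conflict between Table 6-3 and 7.1 arises where the third Grade 2 HFSR would be a third reduction, that is, with no re-escalation in between.

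This should be corrected because it bears on dosing safety and continued access. No test, error rate or sample size is affected. The documents do not give the number of participants at each entry dose, so the share affected is unknown; the SAP expects few patients overall.

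**What to change.** 1. **Table 6-1.** State a minimum dose beneath the table: *80 mg, or the entry dose for participants who enter at 60 mg; a participant who would need less stops regorafenib.* The 80 mg default is the lowest level already listed. If the sponsor prefers to preserve access, add 60 mg as level -3 and make it the minimum for everyone; Section 6 already allows that dose, and 20 mg tablets are supplied.
2. **Tables 6-3 and 6-5.** Replace the 40 mg (one tablet) step with *one dose level (Table 6-1)*. From 160 and 120 mg this is still 40 mg. In the third Grade 2 HFSR row add: *only if Section 7.1 and the minimum dose allow it; otherwise discontinue.*
3. **Section 7.1.** Reword the criterion: *More than two reductions below the rollover starting dose would be needed (a reduction reversed by re-escalation is not counted), or a dose below the Table 6-1 minimum would be needed.* Reword footnote d of Table 6-4 to match.

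The cost is a protocol amendment with a table note (and one row if 60 mg becomes a level) and a few wording changes, with no new procedures. The downside is that participants at the minimum stop at the next event that needs a reduction. Reductions available for entry at 160 / 120 / 80 / 60 mg would be:

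- 80 mg minimum: 2 / 1 / 0 / 0 (160 to 120 to 80; 120 to 80; none; none).
- 60 mg minimum for all: 2 / 2 / 1 / 0 (160 to 120 to 80, where the limit of two applies; 120 to 80 to 60; 80 to 60; none).

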7.1 Discontinuation of Study Intervention

In rare instances, it may be necessary for a patient to permanently discontinue study intervention. If study intervention is permanently discontinued, the participant will not remain in the study. See the SOA for data to be collected at the time of discontinuation of study intervention.

Patients *must* be withdrawn from the study intervention for the following reasons:

- At their own request or at the request of their legally acceptable representative. At any time during the study and without giving reasons, a subject may decline to participate further. The subject will not suffer any disadvantage as a result.

- If, in the investigator's opinion, continuation of the study would be harmful to the subject's well-being.
- At the specific request of the sponsor and in liaison with the investigator (e.g. obvious non-compliance, safety concerns).
- Severe allergic reactions, such as exfoliate erythroderma, anaphylaxis, or vascular collapse.
- Any other potential adverse reaction deemed sufficiently serious to warrant discontinuation of treatment by either the investigator or his designated associate(s).
- Substantial non-compliance with the requirements of the study.
- Use of illicit drugs or other substances that may, in the opinion of the investigator, have a reasonable chance of contributing to toxicity.
- Development of any intercurrent illness or situation which would, in the judgment of the investigator, may affect assessments of clinical status and study endpoints to a relevant degree.
- Clinical progression (e.g. defined as worsening of the ECOG PS ≥ 3 or symptomatic deterioration including increase in liver function tests).
- The development of a second malignancy.
- Subject lost to follow-up.
- Interruption in study drug administration for greater than 28 consecutive days (including the 1 week drug holiday in each cycle).
- More than 2 dose reductions of the study drug are necessary.

Patients with a beta-human chorionic gonadotropin (hCG) test consistent with pregnancy. Pregnancy will be reported as an SAE using the Pregnancy Monitoring Form.

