7.1.2 Rechallenge

Rechallenge should be done according to criteria specified in Section [6.6](#). The interval of drug interruption should not exceed 4 weeks including 1 week break.

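### Section 7.1 requires withdrawal for severe allergic reactions, but Table 6-2 has no exception for them and no rule says which text governs

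*Protocol*

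**What the plan says.** **Protocol Section 7.1** states that patients must "be withdrawn from the study intervention for the following reasons", and one listed reason is "Severe allergic reactions, such as exfoliate erythroderma, anaphylaxis, or vascular collapse". This item carries no investigator-judgment wording. The next item, on other potential adverse reactions, does depend on such a judgment.

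**Protocol Section 6.6** opens with "In case a dose reduction is necessary, the study treatment will be administered according to the following tables". Table 6-2 covers toxicities related to study drug, and its title limits that scope with "Except Hand Foot Skin Reaction, Hypertension, and ALT and/or AST increases". Allergic reactions are not among the title's exceptions. The relevant entries are:
- Grade 3: delay until the event falls to Grade 2 or below, then "Reduce 1 dose level". Re-escalation may be considered in later cycles.
- Grade 4: the same delay and a one-level reduction, with the addition "Permanent discontinuation can be considered at treating" investigator's discretion.
- Footnote a, attached to the table title: "Excludes alopecia, non-refractory nausea/vomiting, non-refractory hypersensitivity, non-clinically significant and asymptomatic laboratory abnormalities".

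**Protocol Section 7.1.2** says "Rechallenge should be done according to criteria specified in Section" 6.6. It makes no exception for patients who meet a mandatory reason in Section 7.1.

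**The concern.** A site facing a severe allergic reaction to regorafenib may look for its instruction in the toxicity table or in the discontinuation list. The two differ on whether the investigator has any discretion, neither refers to the other for allergic reactions, and no precedence is stated.

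What is at stake is mainly re-exposure of a patient after such a reaction. The choice also affects reporting. A patient who is delayed and reduced adds to the frequency of dose modifications, which is the secondary endpoint in Protocol Section 3. A patient who is withdrawn appears among the treatment-emergent events leading to discontinuation in SAP Section 6.6.

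**Working it through.** No arithmetic applies. The trial has no hypothesis test and no sample size calculation, and the documents give no frequency for allergic reactions. The check is to take each type of allergic event and read off what each section directs.

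| Event | Table 6-2 | Section 7.1 | Result |
|---|---|---|---|
| Non-severe, non-refractory hypersensitivity | Out of scope by footnote a | Not covered by the allergic-reaction item | No conflict |
| Severe, non-refractory hypersensitivity | Out of scope by footnote a; no instruction given | Withdrawal required | One explicit instruction; the footnote does not point to it |
| Severe, related, Grade 3, not excluded by footnote a | Delay, reduce one level, re-escalation possible | Withdrawal required | Two instructions that differ |
| Severe, related, Grade 4, not excluded by footnote a | Delay, reduce one level, discontinuation discretionary | Withdrawal required | Two instructions that differ on discretion |

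The conflict is therefore confined to the last two rows.

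- **Grade 3.** This is the clearest case. The row does not mention discontinuation. It arises only through footnote b (no recovery after a 4-week delay, or severe bleeding) and footnote c (cardiac ischemia or infarction). A site that follows the row departs from Section 7.1, and a site that withdraws the patient departs from the row.
- **Grade 4.** A site that withdraws the patient complies with both texts. A site that uses the row's discretion to continue complies with the table and departs from Section 7.1.

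Which row of the comparison an event falls in is itself uncertain. The protocol does not define refractory, and footnote a speaks of hypersensitivity while Section 7.1 speaks of severe allergic reactions with three examples. A site might not class exfoliate erythroderma or vascular collapse as hypersensitivity, and such an event would then stay in the Grade 3 or 4 rows.

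Other pointers do not settle the matter. The Synopsis says treatment continues until the criteria in Section 7.2 are met, but Section 7.2 lists none. Section 4.1 refers to unacceptable toxicity without naming allergic reactions.

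**The case against.** The strongest reply is that the two sections have different jobs. Section 6.6 applies when a dose reduction is needed, so it describes dosing for patients who continue, while Section 7.1 says who may not continue. A specific mandatory item naming anaphylaxis can be read as overriding a general table that never mentions it. Section 7.1 also has two backstops: withdrawal when continuing would be harmful, and withdrawal for any other reaction judged serious enough. A patient withdrawn under Section 7.1 leaves the study, so rechallenge under Section 7.1.2 should not arise.

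That reading is reasonable, and many sites would probably adopt it. But the protocol does not state it, and Table 6-2 is not confined to patients who continue: it addresses permanent discontinuation itself and makes it discretionary at Grade 4. Other parts of Section 6.6 carry their own stopping rules, such as Table 6-4 for Grade 4 hypertension and Table 6-5 for large transaminase increases. A site could expect to find an allergy rule there too. The backstops rest on the investigator's or a designee's judgment, whereas the allergic-reaction item does not.

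A reader might also infer something stronger: that footnote a exempts a treatable anaphylaxis from any dose action, so that one event could lead to withdrawal, to nothing, or to a reduction. The documents do not support this. The footnote limits the scope of the table. It does not say that no action is needed, and it does not switch off Section 7.1. The footnote and the Grade 3 and 4 rows are alternatives, so no single event falls under both. An excluded severe event has one explicit instruction, and a non-excluded one has two.

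The reporting consequence is slight, as the other side would say. Serious events and new Grade 3 and 4 events are collected whatever dose action follows, so the reaction still enters the primary safety endpoint.

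**Conclusion.** The point holds in a limited form. For a related Grade 3 or 4 severe allergic reaction that footnote a does not exclude, Section 7.1 and Table 6-2 give different instructions, most clearly at Grade 3, and the protocol does not say which prevails. For non-refractory hypersensitivity the defect is smaller: the exclusion has no severity limit and no pointer to Section 7.1, although that section still applies if the event is severe.

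The conclusion assumes that the severe reactions in Section 7.1 correspond to Grade 3 or 4, since that section gives no grade. Such events should be rare, but the documents offer no rate, so no expected number can be given. For each event, the statistical effect is at most a move between two descriptive counts: dose modifications and discontinuations. The reason to act is consistency of a safety instruction, not any effect on inference.

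**What to change.** Reconcile the Grade 3 and Grade 4 rows and footnote a of Table 6-2, and Section 7.1.2, with Section 7.1. State expressly whether the table and the footnote cover the reactions named in Section 7.1, and cross-refer the sections so that a single instruction applies to those reactions. The sponsor decides which rule governs; this review takes no position on that.

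The cost is an edit to one table and its footnote, plus cross-references, in a protocol amendment. No extra data or patients are needed.

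### Protocol Table 6-4, footnote d: the stopping condition and its milligram gloss exclude each other under Table 6-1

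*Protocol*

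**What the plan says.** Table 6-1 (Protocol Section 6.6) lists three daily doses: 160 mg as level 0, 120 mg as level -1 and 80 mg as level -2. Nothing is listed below 80 mg.

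Table 6-4 covers hypertension. For a first Grade 3 occurrence it says: "If BP is not controlled with the addition of new or more intensive therapy, reduce by 1 dose level". For a re-occurrence it says: "If Grade 3 hypertension recurs despite dose reduction and antihypertensive therapy, reduce another dose level". Footnote d is attached to the re-occurrence row only: "Subjects requiring >2 dose level reductions (<80 mg reduction) should go off regorafenib".

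Three other places bear on how the footnote is read:

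- Section 6, on the dose carried over from the feeder study: "They will receive either 60, 80, 120, or 160 mg orally".
- The sentence after Table 6-5, for participants reduced within this study: "dose reescalation can be considered up to the starting dose in this rollover study protocol".
- Section 7.1, in the list of reasons for mandatory withdrawal from study intervention: "More than 2 dose reductions of the study drug are necessary". No milligram figure is given there.

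**The concern.** The parenthesis in footnote d appears to restate the level count in milligrams, but under Table 6-1 it describes the opposite end of the scale. The footnote is a stopping condition, so a site that looks to the parenthesis for the operative figure gets a different answer from a site that counts levels. Uniform handling of participants with recurrent Grade 3 hypertension is at stake. Dose-modification counts (the secondary endpoint in Protocol Section 3) and discontinuations (SAP Sections 4.3 and 6.6) would record whatever sites did.

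**Working it through.** **Inputs.** Table 6-1 doses are 160, 120 and 80 mg. Step size: 160 − 120 = 40 mg and 120 − 80 = 40 mg. Cumulative reduction after k levels = 40 × k mg.

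**Reproducing the gloss.** More than two levels means k ≥ 3, so a cumulative reduction of at least 40 × 3 = 120 mg. The printed gloss is a reduction of less than 80 mg, which gives k = 1 only (40 mg). The gloss is not reproduced.

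| Levels down (k) | Dose from 160 mg | Cumulative reduction | More than 2 levels? | Reduction below 80 mg? |
|---|---|---|---|---|
| 1 | 120 mg | 40 mg | no | yes |
| 2 | 80 mg | 80 mg | no | no |
| 3 | 40 mg (not listed) | 120 mg | yes | no |

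No line has yes in both columns.

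**Which lines the footnote reaches.** The re-occurrence row starts from a participant who has already been reduced once and now needs a second reduction. That is k = 2, where neither half of the footnote stops treatment. The halves diverge at k = 3, where only the leading words stop treatment. The k = 1 line belongs to the first-occurrence row, which carries footnotes b and c but not d.

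**Alternative reading: a resulting daily dose below 80 mg.** Section 6 permits four starting doses. Assuming 40 mg steps from each:

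- 160 → 120 → 80 → 40: first below 80 mg at the third step. This matches more than two levels on any count.
- 120 → 80 → 40: first below 80 mg at the participant's second step. Counted from 160 mg, a dose of 40 mg is (160 − 40) / 40 = 3 levels down, which matches. Counted from the participant's own start it is 2 levels, which does not.
- 80 → 40: first below 80 mg at the participant's first step. Again 3 levels from 160 mg, but 1 from the participant's own start.
- 60: already below 80 mg at entry. (160 − 60) / 40 = 2.5, so 60 mg is not a Table 6-1 level on either count.

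Table 6-1 anchors level 0 at 160 mg, whereas the re-escalation sentence after Table 6-5 refers to the participant's starting dose in this study. Footnote d does not say which reference applies.

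**Section 7.1 against the footnote.** The footnote counts dose levels and Section 7.1 counts dose reductions. Because re-escalation is allowed, the two can differ. A participant going 160 → 120 → 160 → 120 → 160 → 120 has had three reductions but stands one level down. Section 7.1 is close to the leading words but is not an exact restatement of them.

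**The case against.** The best counter-argument is that the slip has little room to do harm. At the second reduction, which is what the footnoted row directs, both halves give the same answer. At a third, Table 6-1 offers no listed level and Section 7.1 separately requires withdrawal once more than two reductions are necessary. Table 6-4 is headed as recommended measures, and its footnote a lets the investigator manage hypertension more conservatively. All of this stands, and it limits the point to a minor one.

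A second objection is that the defect rests on one inequality sign read from a PDF by program. If the source prints a reduction greater than 80 mg, the gloss fits more than two levels exactly (40 and 80 mg no, 120 mg yes) and the contradiction disappears. The same line shows both signs, and Table 6-5 prints them distinctly, which makes a misreading less likely but does not verify this character. The source check is therefore needed first.

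A reader might infer that the gloss would take participants off treatment after a single level. The literal words do select a 40 mg reduction, but the row carrying the footnote does not reach that case. A reader might also infer that the safety or tolerability results would be distorted. The documents give no number of affected participants, the analyses are descriptive, and SAP Section 4.1 expects few patients, so no such effect can be shown.

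**Conclusion.** The point holds as a minor internal inconsistency in a stopping rule; it is not a design choice. Under the 40 mg steps of Table 6-1, the two halves of footnote d never select the same participant. Within the row that carries the footnote, they part when a third level (120 mg cumulative) would be needed. Reading the gloss as a resulting dose resolves this without further assumption only for a 160 mg start. For 120 and 80 mg starts it depends on a counting reference that the footnote does not give, and 60 mg has no level. So even a reader who takes the parenthesis for a slip cannot correct it in only one way.

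The conclusion assumes that the sign is printed in the source as extracted, and the resulting-dose comparison assumes 40 mg steps below the listed levels. The number of participants affected cannot be estimated.

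**What to change.** First check the sign in footnote d against the source PDF. If it is confirmed, the sponsor's clinical team should reconcile the parenthesis with the footnote's own leading condition, the re-occurrence row, Table 6-1, the starting doses permitted in Section 6 (including 60 mg) and Section 7.1. The text should also make clear from which dose levels are counted. No dose or threshold is proposed here. The cost is one corrected footnote and a statement of the reference dose, with no change to data collection or analysis.

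One separate item needs the same source check. The Grade 3 row of Table 6-2 reads: "toxicity (\leq Grade 3) recurs, institute permanent dose reduction". As extracted, that includes Grades 1 and 2, for which the Grade 0-2 row of the same table gives no dose change. If the sign is confirmed, those entries also need to be reconciled. The footnote d point does not depend on this.
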